9.3.1. Hematology

Hematology will be collected at screening for all screened subjects, and at Visit 2 Day 8, Visit 5 Day 85 prior to vaccination, and Visit 6 Day 92 for the Safety Lead-In Analysis Set. Hematology tests will include hemoglobin, white blood cell count and differential, and platelet count.

A by-subject listing will also be provided.

9.3.2. Serum Chemistry

Serum chemistry will be collected at the same scheduled visit and timepoints as hematology for the same analysis set. The serum chemistry panel will include sodium, potassium, glucose (random), blood urea nitrogen, creatinine, calcium, albumin, total protein, bilirubin, alanine aminotransferase, and aspartate aminotransferase.

A by-subject listing will also be provided.

9.3.3. Coagulation

Coagulation will be collected at the same scheduled visit and timepoints as hematology for the same analysis set. Coagulation tests will include prothrombin time/international normalized ratio and partial thromboplastin time.

A by-subject listing will also be provided.

9.3.4. Urine Drug Test, Urine Pregnancy Test and Serology

Urine pregnancy tests will be performed at screening, on Day 1/Visit 1 and Day 85/Visit 5 prior to vaccination for female subjects with child bearing potentials. Urine drug test will be performed at screening (exclusion criteria) and may be performed, at the discretion of the investigator, on any subject who experiences an adverse reaction. Serology will be performed at screening only and include hepatitis B, Hepatitis C, and HIV and if positive are a reason for exclusion.

Only a by-subject listing will be provided for urine pregnancy test.

9.4. Vital Sign Measurements

Vital sign measurements are one of the secondary safety endpoints. Vital sign measurements include oral temperature, pulse rate, and diastolic and systolic blood pressure (after subject is seated for at least 5 minutes). Vital signs will be collected at screening and on Days 1/Visit 1 (before vaccine administration and 60 minutes [± 15 minutes] after vaccine administration [before subject is discharged]), Day 8/Visit 2, Day 29/Visit 3, Day 85/Visit 5 (before vaccine administration and 60 minutes [± 15 minutes] after vaccine administration [before subject is discharged]), Day 92/Visit 6, Day 96/Visit 7, and Day 113/Visit 8.

Vital sign measurements will be summarized using descriptive statistics (mean, standard deviation, median, min, max) for reported values and change from baseline at each scheduled visit according to Appendix 13.1. Vital sign measurements will also be summarized as counts and percentages by severity grade (Appendix 13.3).

Summaries will be presented based on treatment arms of BPZE1 prime with BPZE1 boost (A), BPZE1 prime with no boost (B), Total Post BPZE1 prime (A+B), Boostrix prime with BPZE1 boost (C) and Boostrix prime with no boost (D), Boostrix prime (C+D), Total Post Booster BPZE1 (A+C), and Total Post Placebo Boost (B+D), Total Any BPZE1 Exposure (A+B+C) and Total (A+B+C+D).

9.5. Physical Examination

A full physical examination will be completed at screening and will include the following: skin, head, ears, eyes, nose, throat, neck, thyroid, lungs, heart, abdomen, lymph nodes, musculoskeletal system/extremities, and neurological system. Height and weight will be measured at the screening visit only.

A symptom-directed (targeted) physical examination will be performed as mentioned in the schedule of events for all subjects on Day 1/Visit 1 (pre-vaccination), Day 8/Visit 2, Day 29/Visit 3, Day 85/Visit 5 (rep-vaccination), Day 92/Visit 6, Day 96/Visit 7, and Day 113/Visit 8.

A by-subject listing will be provided for physical exam.

10. Interim Analysis

The interim analysis of this study will be purely for monitoring for safety.

A SMC will be convened by ILiAD Biotechnologies to review study progress and participant, clinical, safety, and reactogenicity data, at the following time points:

- After the subjects in the entire safety lead-in cohort (both dose levels) have completed Day 8 (Visit 2). The SMC will review all safety data through Day 8 (reactogenicity and safety laboratory results) and any AEs which have occurred since study initiation.
- Ad hoc when a halting rule is met, for immediate concerns regarding observations

The SMC will review grouped and unblinded data in the closed session only. The SMC will meet and review these data at scheduled time points or ad hoc as needed during this study as defined in the SMC charter. As an outcome of any meeting (after the safety lead-in cohort or with a safety pause), the SMC will make a recommendation as to the advisability of proceeding with study vaccinations (as applicable), and to continue, modify, or terminate this trial.

For analysis on the Safety Lead-In Analysis Set for the Interim Analysis, safety endpoints include

- Solicited local, nasal/respiratory, and subjective systemic reactogenicity adverse event by toxicity grade at post-prime vaccination on Day 1, and on each of the 8 days following vaccination.
- Treatment-emergent adverse events (TEAEs) occurred since study initiation, and their relatedness to vaccination, severity, and serious TEAE.
- Laboratory and vital sign tests and toxicity grade at each scheduled visit.

Tables will be provided based on the safety lead-in analysis set by treatment arms of BPZE1 10^7 CFU, BPZE1 10^9 CFU, and Boostrix. Tables will be provided for

- subject disposition,
- demographics,
- Solicited local, nasal/respiratory, subjective systemic reactogenicity on each day (Appendix 13.1) by toxicity grade based on FDA standard (Table 9-1).
- Overview of TEAE, TEAE by SOC/PT, TEAE by severity grade, SAE, and SAE related to study vaccination.
- Change from baseline of laboratory test (hematology and serum chemistry) and vital sign tests on Day 2 (Visit 2)
- Summary of laboratory and vital sign tests by toxicity grade on Day 8 (Visit 2) (Appendix 13.2, 13.3)
- By-subject listing will also be provided to support the above tables. In addition, a by-subject listing of IP administration will also be provided.

11. Changes in the Planned Analysis

The SAP contains no changes in the planned analyses described in the protocol.

12. References

Department of Health and Human Services (DHHS), Food and Drug Administration, Center for Biologics Evaluation and Research (US). Guidance for industry: Toxicity grading for healthy adult and adolescent volunteers enrolled in preventive vaccine clinical trials. September 2007 [cited 2017 Nov 29]. Available from: <https://www.gpo.gov/fdsys/pkg/FR-2007-09-27/pdf/E7-19155.pdf>

ILiAD Biotechnologies. BPZE1. Investigator's brochure, 0.42 ed. Weston (FL); 2017. 44 p.

13. Appendices

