Recent decades have witnessed a sharp increase in cases and it is generally agreed that there is a critical need for a new and more effective vaccine targeting *B. pertussis*. In 2014, it was estimated there were 24.1 million pertussis cases and 160,700 deaths from pertussis in children younger than 5 years of age, with 53% of the estimated deaths being in infants younger than 1 year (Yeung et al 2017). With the current acellular vaccines being ineffective against colonization (and therefore transmission) there is little to any herd immunity that can develop, leaving infants at risk for acquiring pertussis from close contacts. As a potential solution to this problem, the BPZE1 vaccine has been developed to be given as a single intranasal administration. Unlike existing vaccines, BPZE1 has the potential to prevent transmission of *B. pertussis* from siblings and adults to neonatal infants. While ultimately intended for vaccinating neonatal infants, a nearer term solution is to immunize adults and adolescents with BPZE1 to prevent transmission of *B. pertussis* to vulnerable infants.

BPZE1 was engineered by genetically altering or removing 3 *B. pertussis* toxins: pertussis toxin (PT), tracheal cytotoxin (TCT), and dermonecrotic toxin (DNT). Genetic stability of liquid BPZE1 formulation was demonstrated in vitro and in vivo.

A Phase 2a clinical study is being conducted to compare 2 doses (10^7 and 10^9 CFU) of the lyophilized formulation of BPZE1, delivered by the VaxINator™ conical-shape atomization device connected to a 1-mL syringe. This study will assess the new lyophilized formulation of the BPZE1 vaccine to be evaluated in US adults and will provide an opportunity to characterize the immunological response of 2 different dosages delivered by nasal immunization. For this Phase 2b study, the BPZE1 experimental vaccine will be supplied in a lyophilized vial for reconstitution prior to intranasal administration via the VaxINator atomization device. Two lyophilized BPZE1 experimental vaccine doses, 10^7 CFU and 10^9 CFU, will be evaluated in the safety lead-in cohort of the 2b study with subjects continuing with the same intranasal dose level through the booster (10^7 CFU or 10^9 CFU). The dose targeted for the remainder of the subjects in the Phase 2b study will be 10^9 CFU unless a safety concern arises and the Safety Monitoring Committee (SMC) recommends proceeding with the 10^7 CFU dose only.

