
The first 48 subjects randomly assigned will be designated the safety lead-in cohort and will be sequentially enrolled by escalating dose. The first 24 subjects will be randomly assigned as noted above in a ratio of 2:1 to receive active product of either an intranasal dose of 10^7 CFU of BPZE1 or IM Boostrix. These subjects will be followed through Day 8 with safety laboratory tests, reactogenicity, and AE assessments with daily review by the medical monitor for activation of any halting rule. Following accumulation of all safety data through Day 8 post-vaccination, the 24 additional subjects will be randomly assigned 2:1 to receive active products of either an intranasal dose of 10^9 CFU of BPZE1 or IM Boostrix. To maintain the blind for intranasal and IM administered products, all subjects will receive appropriate placebo vaccinations. All safety lead-in subjects will have safety laboratory testing at baseline (screening), and on Days 8, 85 (prior to vaccination), and 92. The medical monitor has the authority to request a review by the SMC should a halting rule be initiated or there are any other safety concerns. The SMC will convene after the subjects in the entire safety lead-in cohort (both dose levels) have completed Day 8 (Visit 2) and will review all safety data through Day 8 (reactogenicity and safety laboratory results) and any AEs which have occurred since study initiation. The SMC will be authorized to allow the remainder of the subjects to be randomly assigned (see Table 3-2). The randomization scheme for the safety lead-in will follow the same scheme as the full cohort for the second vaccination (keeping at either 10^7 CFU or 10^9 CFU based on initial dosing assignment) such that half the BPZE1 and half the Boostrix vaccinated subjects will receive intranasal BPZE1 vaccination on Day 85 and the other half will receive placebo.

Table 3-2 Dosing and Safety Lead-In Cohort

BPZE1 Dose	BPZE1	Boostrix	Trigger to advance	Review Process	Advancing to
10^7	N = 16	N = 8	Day 8 safety on 10^7 dosing cohort	Pause rules; daily medical monitor reviews	10^9 safety lead-in
10^9	N = 16	N = 8	Day 8 safety on full safety lead-in cohort; all adverse events to date	Safety Monitoring Committee review	Full cohort

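### The by-dose TEAE tables for the safety lead-in review compare columns with unequal follow-up, which biases crude percentages at 10^9 CFU low relative to 10^7 CFU and pooled Boostrix

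*SAP*

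**What the plan says.** SAP Section 3.1 makes the lead-in sequential: "The first 48 subjects randomly assigned will be designated the safety lead-in cohort and will be sequentially enrolled by escalating dose". The second step waits for the first: "Following accumulation of all safety data through Day 8 post-vaccination, the 24 additional subjects will be randomly assigned 2:1". Table 3-2 gives 16 BPZE1 and 8 Boostrix subjects at each step.

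The SMC convenes once both dose levels have completed Day 8 (SAP Section 10; Protocol Sections 3.1 and 11.1.1.1). It reviews reactogenicity and laboratory results through Day 8, but adverse events without a common cut-off: "any AEs which have occurred since study initiation". The matching safety endpoint in SAP Section 10 is "Treatment-emergent adverse events (TEAEs) occurred since study initiation, and their relatedness to vaccination, severity, and serious TEAE". On layout, SAP Section 10 states: "Tables will be provided based on the safety lead-in analysis set by treatment arms of BPZE1 10^7 CFU, BPZE1 10^9 CFU, and Boostrix". The adverse event tables are "Overview of TEAE, TEAE by SOC/PT, TEAE by severity grade, SAE, and SAE related to study vaccination".

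The TEAE definition in SAP Section 9.2 has no upper time limit. All-cause events are collected to Day 29 after the prime dose, and related and serious events continue after that. Neither document plans a common-window TEAE table, a person-time rate or a follow-up summary for this review.

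**The concern.** The SMC uses this review to release the remaining subjects for randomisation. SAP Section 1 and Protocol Section 1.1 set 10^9 CFU for the full cohort "unless a safety concern arises and the Safety Monitoring Committee (SMC) recommends proceeding with the 10^7 CFU dose only". A by-dose TEAE table is a natural thing to read when asking whether such a concern exists.

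If the 10^7 column has collected events for longer, its crude percentage is higher even when the two doses carry the same risk, and a true excess at 10^9 is diluted in the contrast. The Boostrix column does not correct for this. It pools 8 subjects from the early step with 8 from the late step, so its follow-up matches neither dose.

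**Working it through.** **Plan's own figures.** 24 × 2/3 = 16 BPZE1 and 24 × 1/3 = 8 Boostrix per step; 2 × 24 = 48 in total; pooled Boostrix 8 + 8 = 16. These agree with Table 3-2. The documents state no follow-up time at the review.

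**Timeline.** Take the last 10^7 vaccination as time 0. Let w be the enrolment span of each cohort, g the gap between the 10^7 Day 8 data and the first 10^9 vaccination, and L the lag from the last 10^9 subject's Day 8 to the data cut, all in days. Day 8 is 7 days after vaccination. Follow-up at the cut is then:

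- 10^7: from 14 + g + w + L to 14 + g + 2w + L
- 10^9: from 7 + L to 7 + w + L

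With w = g = L = 0 this is 14 against 7 days. Pooled Boostrix averages (14 + 7)/2 = 10.5 days, which is 1.5 times the 10^9 figure. If the last 10^9 visit uses the full +3 days of the Visit 2 window (Table 13-1), it is 17 against 10 days, a ratio of 1.7.

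**Displayed percentages.** The documents give no expected rate of unsolicited events or enrolment speed, so the following are assumptions: even enrolment, a 28-day risk of 40% with constant hazard h = −ln(0.6)/28 = 0.01824 per day, and follow-up capped at 28 days for all-cause events. Risk by day t is 1 − exp(−ht), or 1 − exp(−2ht) for a doubled hazard, averaged over subjects.

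| w | g | L | Mean days 10^7 / 10^9 | Ratio | Equal risk: 10^7 / 10^9 | Doubled hazard at 10^9 |
|---|---|---|---|---|---|---|
| 0 | 0 | 0 | 14.0 / 7.0 | 2.0 | 22.5% / 12.0% | 22.5% |
| 0 | 7 | 0 | 21.0 / 7.0 | 3.0 | 32% / 12% | 23% |
| 7 | 3 | 0 | 26.9 / 10.5 | 2.6 | 39% / 17% | 32% |
| 14 | 3 | 0 | 28.0 / 14.0 | 2.0 | 40% / 22% | 39% |
| 28 | 3 | 0 | 28.0 / 20.1 | 1.4 | 40% / 30% | 50% |
| 7 | 3 | 3 | 27.9 / 13.5 | 2.1 | 40% / 22% | 39% |
| 7 | 3 | 7 | 28.0 / 17.5 | 1.6 | 40% / 27% | 47% |
| 7 | 3 | 14 | 28.0 / 24.5 | 1.14 | 40% / 36% | 59% |
| 0 | 0 | 14 | 28.0 / 21.0 | 1.33 | 40% / 32% | 54% |

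How the cap enters, for w = 7, g = 3, L = 0: 10^7 follow-up runs from 24 to 31 days. Four sevenths of subjects average 26 days and three sevenths are held at 28, so the mean is 26.9. For w = 28 with L = 14, the 10^9 mean is 0.25 × 24.5 + 0.75 × 28 = 27.1 days and the ratio is 28/27.1 = 1.03.

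The cap does not apply to related or serious events. For those, with no gap and no lag, the ratio of means is 24.5/10.5 = 2.33, 35/14 = 2.50 and 56/21 = 2.67 at 7, 14 and 28 days of enrolment. A 14-day lag takes the first of these to 38.5/24.5 = 1.57.

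**Timing of events.** In the w = 7, g = 3, L = 0 case, if half of the 28-day hazard falls in the first 7 days, equal risk shows as 39% against 26%. If all of it falls there, both columns show 40% and there is no distortion.

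**With a Day 8 cut.** Every subject contributes 7 days, so the follow-up ratio is 1.0 and equal hazards give equal expected percentages. Expected counts under a doubled hazard are 16 × 0.225 = 3.6 at 10^9 against 16 × 0.120 = 1.9 at 10^7. A two-sided Fisher test at 5% would be significant about 5% of the time.

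**The case against.** Much of the case on the other side stands.

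- **No data-cut date is fixed.** The documents say only that the SMC convenes after Day 8 is complete. A lag adds the same days to both cohorts and shrinks the ratio. A reader might infer that 10^7 always has at least twice the follow-up, or that a dose with twice the hazard would still look better. Neither is supported. The factor of two compares nominal minimum with nominal minimum, and with a 7-day lag or 28-day enrolment the doubled hazard shows as higher at 10^9 (47% or 50% against 40%).
- **The 10^9 column is not wrong in itself.** It is correct for the time it covers. A reader might infer that the review as a whole makes 10^9 look safer than it is. The documents support only a biased contrast with the other two columns, in the TEAE and SAE tables. Solicited reactions by day, and laboratory and vital-sign tables at Visit 2, are on matched windows.
- **No rule compares doses.** The halting rules in Protocol Section 6.4 use single events, small counts or 5% of subjects with the same severe reaction.
- **The SMC has other information.** By-subject and product-administration listings accompany the tables, so a matched window could be rebuilt. The SMC may request more data, and its charter, which is not available here, may define further elements. Protocol Section 11.1.1.1 also has it review SAEs regularly, so this is the only review with a specified time, not the only safety review.
- **The cumulative view is required.** Protocol Sections 3.1 and 11.1.1.1 call for all events since initiation. Reducing the cumulative tables to a listing would take later related and serious events out of the tables.

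None of this makes the planned by-dose percentages comparable. After Visit 2 the next scheduled visit is Day 29, so events in between depend largely on subjects making contact. That may narrow the 10^7 excess, but it adds uneven ascertainment. Day 1 to Day 8 is the window in which all 48 subjects are followed alike.

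**Conclusion.** The concern holds for the by-dose TEAE and SAE tables in SAP Section 10. Sequential enrolment and the Day 8 gate produce unequal follow-up by design, and crude percentages at 10^9 are biased low relative to 10^7 and pooled Boostrix unless events cluster in the first 7 days.

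The direction follows from the documents; the size does not. For all-cause events the ratio of mean follow-up is about 1.4 to 3.0 with no lag. It is between 1.03 and 1.33 with a two-week lag, and nearest 1 when enrolment is also slow. The displayed percentages rest further on the assumed 40% risk and the assumed hazard shape. The main analyses of the trial are untouched. The change is worth making because it is nearly free and bears on the one SMC review whose timing is specified.

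**What to change.** In SAP Section 10:

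1. Keep the cumulative TEAE and SAE tables, and show days of follow-up (total and mean) for each column.
2. Add by-dose TEAE tables (overview, SOC/PT, severity, related, serious) with onset restricted to Day 1 to Day 8 for every lead-in subject.
3. Show Boostrix split by dose step (8 + 8), so that each BPZE1 dose can be read against its concurrent controls.
4. State the data-cut date rule for the review.

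The cost is SAP wording, a date filter on planned tables and one extra set of tables; no new data are needed. With 16 subjects per dose, the change removes a bias but gives little power to detect an excess, and the SAP should not suggest otherwise.

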13.1. Schedule of Study Procedures

Table 13-1

Procedure	Screening	Treatment Period									
		0	1	2	3	4	5	6	7	8	9
Study visit											
Days relative to most recent vaccination	-30 to 0	1	8	29	78	85/1	8	12	29	85	169
Days relative to first vaccination^b	-30 to 0	1	8	29	78	85	92	96	113	169	254
Window allowance	30	0	+3	+7	-7	+10	+2	+/-2	+7	-7	±15
Informed consent	X										
Inclusion/exclusion criteria	X	X ^c				X ^c					
Demographic and baseline data ^d	X										
Medical history ^e	X	X ^c				X ^c					
Medication ^f	X	X	X	X	X	X	X	X	X	X ^g	X ^g
Serology ^h	X										
Urine drug screen	X										
Physical examination ⁱ	X	X ^j	X	X		X ^j	X	X	X		
Vital sign measurements	X	X ^k	X	X		X ^k	X	X	X		
Safety laboratory tests for enrollment ^l	X										
Safety laboratory tests for safety cohort ^m	X		X			X ⁿ	X				
Urine pregnancy test (female subjects of childbearing potential)	X	X ⁿ				X ⁿ					
Randomization		X									
Vaccination ^o		X				X					
Subject diary dispensing ^p		X				X					
Subject diary reviewed ^q			X				X				
Reactogenicity - post vaccination		X ^r	X ^s			X ^r	X ^s				
Immunogenicity laboratory tests for serumpertussis IgG and IgA ELISA		X ⁿ		X		X ⁿ			X	X	X
Mucosal pertussis nasal antibody testing (S-IgA ELISA) – nasal absorption device ^t	X ^u			X	X				X	X	X
Nasal collection for B. pertussis colonization					X ^v		X	X	X ^v		X ^w
PBMC for cellular immunity (subset of no more than 60 subjects)		X	X				X				

Collection of serious adverse events and adverse events of special interest only x										X	X
Adverse events xy		X	X	X	X	X	X	X	X		
End-of-study form completion											X

Abbreviations: ELISA, enzyme-linked immunosorbent assay; Ig, immunoglobulin; PBMC, peripheral blood mononuclear cell; S-IgA, secretory immunoglobulin A.

- a End-of-study Visit.
- b Days relative to vaccination are only estimates as the window allowance is not inclusive. Should a study pause occur than vis its/windows will be adjusted to allow for subjects to continue without protocol deviation. Visit schedule following the boosting vaccination is calculated relative to the day the boosting vaccination was received.
- c Inclusion/exclusion criteria and medical history will be reviewed and updated on Day 1 and Day 85 with specific vaccination exclusions applied.
- d Including date of birth (day, month, and year), sex, race, ethnicity, weight, height, and body mass index(derived).
- e Including prior and concomitant medical conditions, surgeries significant procedures.
- f Concomitant medications include all medications (including vaccines) taken by the subject from the time of signing the informed consent through 28 days after the boosting vaccination (or through early termination visit if prior to that time).
- g Only medications associated with serious adverse events.
- h Serology testing will include hepatitis B, hepatitis C, and human immunodeficiency virus.
- i Full physical examination at screening; symptom-directed (targeted) physical examination at all other scheduled time points. Interim physical examinations will be performed at the discretion of the investigator, if necessary. Height and weight will be measured at screening only.
- j On Day 1 (Visit 1) and 85 (Visit 5), targeted symptom-directed physical examination will be performed before vaccine administration.
- k On Day 1 (Visit 1) and 85 (Visit 5), vital sign measurements will be collected once before vaccine administration and at 60 minutes (± 15 minutes) after vaccine administration (before subjects are discharged).
- l Safety laboratory testing for safety cohort include (Table 13-2) hemoglobin, white blood count with differential, platelet count, sodium, potassium, random glucose, blood urea nitrogen, creatinine, calcium, albumin, total protein, bilirubin, alanine aminotransferase, aspartate aminotransferase, prothrombin time, and partial thromboplastin time. See Table 13-2 for specific laboratory tests to utilize for exclusion for the full cohort (kidney, hepatic, and hematology/coagulation only). Laboratory testing may be repeated once during the 30-day screening period if specific values used for exclusion criteria exceed toxicity Grade 1, with the last value being the value of record.
- m The first 48 subjects randomly assigned will be designated the safety lead-in cohort and safety laboratory testing will be performed in this subset beyond the screening visit. Should any laboratory value result in a grade 3 or greater toxicity score this lab must be entered as an adverse event and followed with retesting and observing for resolution or new clinical baseline.
- n Performed prior to vaccination.
- o Subjects will be randomly assigned as per Table.
- p All subjects will record reactogenicity in the daily subject diary starting on the same day of the prime (Day 1) and boosting (Day 85) vaccinations and for additional days (not counting vaccination day).
- q The clinical staff will review the information from the subject diary with the subjects on Days 8 and 92. Toxicity grading will be applied by investigator for all subject recorded reactogenicity on days 1-8.
- r Reactogenicity will be collected on Day 1 (Visit 1) and 85 (Visit 5) at 60 minutes (± 15 minutes) after dose administration (before subjects are discharged).
- s To be collected from day of vaccination through additional 7 days post-vaccination by subject.

- ^t Must occur at least 6 days prior to intranasal vaccination.
- ^u Collected but only tested within the trial if the subject is randomly assigned into the study. Samples may be used per subject consenting for additional product development needs.
- ^v To be collected after mucosal pertussis nasal antibody collection.
- ^w Only in subjects who tested positive by pertussis culture at Day 113. Any subject who remains positive on Day 254 will be provided a short course of azithromycin.
- ^x At the discretion of the investigator a urine drug screen may be performed on any subject who experiences an adverse event.
- ^y All adverse events will be collected 28 days after each vaccination. Adverse events related to vaccination will be collected through Day 113

